#### Multiplicity of testing

Due to the exploratory nature of the sub-study, no adjustment for multiplicity of testing will be done. The p-value will be used to assess the significance of the results.

#### Analysis of secondary clinical and diagnostic parameters

Dermal trypanosomes may be the cause of dermatitis and/or pruritus, therefore a secondary clinical and exploratory question of interest is:

Does acoziborole reduce the occurrence at 4 months of dermatitis and/or pruritus signs or symptoms in comparison with placebo?

The secondary clinical parameter will be the occurrence/presence of dermatitis and/or pruritus signs or symptoms at 4 months.

The same approach as for the primary diagnostic parameter will be used for the occurrence of dermatitis or pruritus.

Current specific molecular diagnostic methods are known to be of low sensitivity. The TrypSkin sub-study aims at testing new methods to overcome this weakness.

Secondary diagnostic parameters will be the occurrence of IHC+ results in skin, TBR-PCR+ and/or 18S-PCR+ in blood and/or skin, as well as novel diagnostic parameters corresponding to occurrence of positive results by qPCRs, multiplex RT-qPCRs and SHERLOCK in blood and/or skin.

The secondary analyses will be exactly the same as the primary diagnostic parameters.

## Properties of diagnostic tests

Results of the following tests, alone or in combination, will be analysed in both groups at enrolment to assess the specificity, sensitivity, positive and negative predictive values of the new qPCRs, multiplex RT-qPCRs, and SHERLOCK in blood and/or skin:

- 1) TgSGP-PCR in skin (primary diagnostic parameter) and,
- 2) IHC in skin; TBR-PCR and 18S-PCR in blood and/or skin (secondary diagnostic parameters)

Results of all the new molecular tests, alone or in combination, will also be analysed in the placebo group at 4 months to test their repeatability.

Based on the placebo group data, the association between baseline and 4 months diagnosis results will be estimated through Cramer V coefficient for each diagnostic test and combination of diagnostic tests. The test or combination of tests providing the best association (reproducibility of baseline result) will be used for ranking tests. Other properties: sensitivity, specificity, predictive value, cost and rapidity for obtaining a response will also be used for ranking tests. Multicriteria ranking (sum of ranks) will be performed and the primary analysis will be redone on this new reference (best multicriteria rank) and each diagnostic test property will be computed with respect to this new reference.

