## 2.1.3. Exploratory objectives (TrypSkin sub-study)

- To estimate the prevalence of extravascular dermal *T.b. gambiense* in seropositive individuals non-confirmed parasitologically (16).
- To compare the properties (sensitivity, specificity, accuracy, positive predictive value, negative predictive value, and repeatability) of different methods of detection of *T. brucei s.l.* and *T.b. gambiense* (polymerase chain reactions [PCRs], quantitative PCRs [qPCRs], multiplex Quantitative Reverse Transcriptase [qRT]-PCRs, Specific Highsensitivity Enzymatic Reporter unlocking [SHERLOCK], immuno-histochemistry [IHC]) in skin biopsies and blood samples.
- To determine the presence/absence of extravascular *T.b. gambiense* in skin biopsies of all subjects at enrolment, and at the end of the study.
- To assess the effectiveness of acoziborole on elimination of extravascular *T.b. gambiense* parasites in dermis with the methods or combination of methods, contingent on having better validity than *Trypanosoma brucei gambiense*-specific glycoprotein PCR (TgSGP-PCR) and provided that the prevalence of dermal trypanosomes by any method at baseline is greater than 2%.

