5.3.6. Properties of diagnostic tests Analysis

Considering successively the results of (1) TgSGP-PCR in skin (primary diagnostic parameter), and (2) IHC, TBR-PCR and/or 18S-PCR in skin (secondary diagnostic parameters), as validated diagnostic methods, the relative specificity, relative sensitivity, positive and relative negative predictive values of multiplex qPCRs, multiplex RT-qPCRs and SHERLOCK on skin, blood and DBS will be analyzed at enrolment. Four analyses will be performed for skin, blood, DBS and considering the result of any of the three samples.

Based on the placebo group data, the association between baseline and 4 months diagnosis results will be estimated through Cramer V coefficient for each diagnostic test and combination of diagnostic tests. The test or combination of tests providing the best association (reproducibility of baseline result) will be used for ranking tests. Other properties: relative sensitivity, relative specificity, predictive values, Cohen Kappa coefficient will also be used for ranking tests alone or in combination. Multicriteria ranking (sum of ranks) will be performed and the primary analysis will be redone on this new reference (best multicriteria rank) and each diagnostic test property will be computed with respect to this new reference.

6. Statistical software

All statistical analyses and generation of TLFs will be done using SAS software. Copyright © 2016 SAS Institute Inc¹¹.

7. Shell Tables, Listings and Figures (Attached separately)

8. References

- 1. International Conference on Harmonisation; Guidance on Statistical Principles for Clinical Trials *E9; Availability--FDA. Notice.* Vol 63.; 1998.
- 2. International Conference on Harmonisation: Structure and Content of Clinical Study Reports E3, Japan and USA.; 1995.
- 3. Investigator Brochure Acoziborole V4.0 12 November 2019.

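### The rank-sum winner's enrolment accuracy is estimated in the same subjects that selected it, without correction, so its agreement with the reference test can be overstated

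*Protocol*

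**What the plan says.** Protocol 10.8 (Properties of diagnostic tests) and SAP 5.3.6 assess the new qPCR, RT-qPCR and SHERLOCK assays at enrolment. The references are first TgSGP-PCR in skin, then IHC, TBR-PCR and 18S-PCR.

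The tests and combinations are then ranked. One criterion is repeatability: "Based on the placebo group data, the association between baseline and 4 months diagnosis results will be estimated through Cramer V coefficient". For the others the documents differ. The protocol has "Other properties: sensitivity, specificity, predictive value, cost and rapidity for obtaining a response will also be used for ranking tests". The SAP has "Other properties: relative sensitivity, relative specificity, predictive values, Cohen Kappa coefficient will also be used for ranking tests alone or in combination". The SAP thus drops cost and rapidity, which do not depend on subjects' results, and adds kappa, so every criterion it lists is estimated from sub-study data.

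The candidate with the best rank sum becomes the new reference, and the primary exploratory analysis is redone on it: "Multicriteria ranking (sum of ranks) will be performed and the primary analysis will be redone on this new reference (best multicriteria rank". In the same sentence, "each diagnostic test property will be computed with respect to this new reference".

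No hold-out sample, cross-validation, bootstrap or selection-adjusted interval is described. SAP 3.1 provides ordinary two-sided 95% intervals. On multiplicity, Protocol 10.8 says: "Due to the exploratory nature of the sub-study, no adjustment for multiplicity of testing will be done".

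**The concern.** Each candidate's estimated accuracy is its true agreement with the reference plus sampling error. Taking the best of many favours candidates whose error happened to be favourable, so the winner's own estimate tends to be too high. Declining a multiplicity adjustment deals with type I error. It does not deal with bias in a reported estimate.

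Comparing test properties is a stated exploratory objective, so these figures are a result in their own right. Low prevalence makes the problem larger, and the plan allows for it: the 20-25% figure is an upper hypothesis from limited Guinea data, and the effectiveness objective stays open for any baseline prevalence above 2%.

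The point is confined to the accuracy reported at enrolment. It does not concern the Month 4 treatment comparison.

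**Working it through.** **Inputs from the documents.** There are 690 evaluable subjects (Protocol 10.1.1, SAP 2.4.2). Planning prevalence is 20% and allocation is 175 placebo to 525 acoziborole (Protocol 10.1.2). The prevalence floor for the effectiveness objective is 2% (Protocol 2.1.3). The number of candidates is not stated. Protocol 8.4 names three new methods on three sample types, so at least 3 × 3 = 9 before combinations.

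**Assumed, because the documents give no figures.** 10 or 30 candidates, each with sensitivity 80% and specificity 95%; latent correlation between tests 0 or 0.5; baseline-to-Month 4 latent correlation 0.8; 1,500 runs per scenario.

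**1. The plan's own figure.** n = z²p(1−p)/d² = 1.96² × 0.20 × 0.80 / 0.03² = 682.9, so 683. The stated 690 is within about 1%.

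**2. Sampling error available to selection.** Reference positives number 690 × 0.20 = 138, 690 × 0.05 = 34.5 and 690 × 0.02 = 13.8. The standard error of a sensitivity of 80% is √(0.8 × 0.2 / positives), which gives 3.4, 6.8 and 10.8 points.

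**3. Equally good candidates, SAP criteria.** The ranking uses placebo Cramer V, sensitivity, specificity, PPV, NPV and kappa. The table shows the winner's apparent minus true value in points, over 10 to 30 candidates and correlation 0 to 0.5, with an error-free reference.

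| Prevalence | Sensitivity | PPV | Kappa × 100 |
|---|---|---|---|
| 20% | 3.1 to 4.7 | 3.1 to 4.5 | 3.8 to 5.7 |
| 5% | 6.1 to 9.0 | 5.7 to 8.3 | 6.4 to 9.6 |
| 2% | 9.8 to 13.9 | 5.4 to 7.7 | 7.2 to 10.4 |

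For sensitivity this is roughly 0.9 to 1.4 of the standard errors in step 2. A single prespecified test shows no upward bias beyond 0.4 points. A separate simulation with nine tests, Cramer V included, gave about 3-6, 8-10 and 13 points of sensitivity at the three prevalences.

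**4. Protocol criteria instead.** Kappa is removed, and cost and rapidity enter as random ranks (10 candidates, correlation 0.5, 20% prevalence). The winner's sensitivity / PPV / kappa × 100 are 82.7 / 82.8 / 78.4, against 83.0 / 83.0 / 78.7 under the SAP criteria and true values of 80 / 80 / 75.

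**5. Candidates that truly differ (probit SD 0.3 to 0.6).** Across sensitivity, PPV and kappa the bias falls to 0.4 to 1.4 points at 20% prevalence and 2.4 to 7.8 points at 2%.

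**6. Insensitive reference, 20% prevalence.** True PPV for infection is 0.16 / (0.16 + 0.04) = 80%; true kappa × 100 is 75.

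| Reference sensitivity | PPV, one prespecified test | PPV, winner of 10 / 30 | Kappa × 100, winner of 10 / 30 |
|---|---|---|---|
| 50% | 40.0 | 42.9 / 43.4 | 50.2 / 51.1 |
| 70% | 55.9 | 59.0 / 60.0 | 63.0 / 64.4 |
| 90% | 71.9 | 75.2 / 76.0 | 74.1 / 75.1 |

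Selection raises apparent PPV by about 3 to 4 points, yet it stays below 80%. Apparent kappa only reaches its infection value when the reference is 90% sensitive.

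**7. Source of the bias.** With selection in one half and estimation in the other (10 candidates, correlation 0.5), sensitivity is 79.9%, 80.2% and 80.3% at 20%, 5% and 2% prevalence, against a true 80%.

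**8. After the switch.** With winner W as the reference, W's sensitivity is n(W+)/n(W+) = 100%, and its PPV and kappa are perfect in the same way. A combination (W or X) has sensitivity 100% against W. A combination (W and X) has specificity and PPV 100%. None of these is a measurement.

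**The case against.** The strongest reply is that nobody is misled about infection. A reader might infer that the winning test will be credited with more accuracy for true infection than it has. The documents do not support that. The SAP labels sensitivity, specificity and NPV as relative (though not PPV), and Protocol 10.8 concedes that current specific molecular methods are insensitive.

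Take a test with sensitivity 70% and specificity 97%, and a reference with 60% and 99.5%, errors independent, at 20% prevalence. Both are positive in 0.2 × 0.7 × 0.6 + 0.8 × 0.03 × 0.005 = 0.0841, and the test is positive in 0.14 + 0.024 = 0.164. PPV against the reference is 0.0841 / 0.164 = 51%, while PPV for infection is 0.14 / 0.164 = 85%. A few points of optimism do not close that gap. This stands, and it limits the point to agreement with the reference.

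It is also fair that the size depends on assumptions. If the tests differ clearly and prevalence is near the planning value, the bias is small.

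Third, the sub-study is exploratory, properties are analysed for all the new methods and not only the winner, and the main TgSGP-PCR analysis is untouched. That keeps the priority low. It does not remove the bias from the winner's figures.

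Finally, a reader might infer that the winner's optimistic figures open the effectiveness analysis, because Protocol 2.1.3 plans it "with the methods or combination of methods, contingent on having better validity than" TgSGP-PCR. The comparison there is with TgSGP-PCR, and neither document says that the rank-sum winner's enrolment figures decide it.

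**Conclusion.** The point holds in limited form. Selection and estimation share the same subjects without correction, so the winner's relative sensitivity, PPV and (SAP only) kappa against the chosen reference can be overstated. The documents do not fix the amount. Under the assumed accuracies it runs from about 1 point (clearly different tests, 20% prevalence) to about 14 points of sensitivity (equally good tests, 2% prevalence). An unconditional statement that the figures are overstated by a given amount would go too far.

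The circularity after the switch needs no assumption: if the winner is included when properties are recomputed, its figures against itself are perfect by construction. The matter is of low priority, being a refinement to an exploratory analysis.

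**What to change.** In SAP 5.3.6:

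- Resample subjects with replacement within arm (for example 1,000 times) and repeat the full SAP ranking in each resample, including the placebo Cramer V. This needs a written list of candidate tests and combinations.
- Report optimism-corrected relative sensitivity, relative specificity, predictive values and kappa for the winner beside the apparent values, and how often each candidate wins.
- State that the correction is partial and that all figures are relative to the reference. In one simulation (80 datasets, 60 resamples each) the bootstrap removed roughly 50 to 90% of the bias, leaving about 1-2 points of sensitivity at 20% prevalence and 2-6 at 5%. Splitting the sample removes it more fully but halves the positives.
- After the switch to the new reference, do not report the winner's properties against itself, or against any combination containing it, as accuracy.

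The cost is a little more programming on data already collected, and somewhat less favourable reported accuracy. No visit, sample, primary safety analysis or TgSGP-PCR analysis changes.

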## 8.4. Exploratory assessments

For subjects participating in the TrypSkin exploratory sub-study, the following samples will be taken at screening (baseline) and 4 months (EoS):

- 3 mL fresh blood (in nucleic acid-preservative buffer) and 5 DBS
- Two 2 mm-skin-punch biopsies on the right back shoulder under local anaesthesia

Samples will be shipped to specialised partner laboratories (Institut National de Recherche Biomédicale [INRB], Institut Pasteur Guinea and Institut Pasteur Paris and Institute of Tropical Medicine [ITM] Antwerp) for the following analyses:

1- Molecular detection of trypanosomes:

- Common automatised extraction of total nucleic acids (TNAs) from fresh blood, DBS and skin biopsies
- On TNAs from fresh blood and skin (main validated diagnostic methods):
  - For all samples: TBR-PCR and 18S-PCR (*T. brucei s.l.*)
  - For TBR-PCR+ and/or 18S-PCR+ samples: T.b. gambiense-specific TgSGP-PCR
- On TNAs from fresh blood, DBS and skin (additional methods to be tested):
  - o qPCR detection using at least 2 targets
  - Multiplex RT-qPCR detection using novel targets
  - CRISPR-derived approach (SHERLOCK)
- 2- Immuno-histochemical detection of dermal trypanosomes:
  - At least 2 automatised IHC on Formalin-Fixed Paraffin-Embedded (FFPE) skin sections for all subjects with *T. brucei*-specific staining (Anti-Invariable Surface Glycoprotein 65 [ISG65] and Anti-cross reacting determinant [CRD] and secondary polymer amplification
  - Automatised acquisition and double *in silico* blind reading, pictures annotation and archiving
- 3- Preliminary tests for the detection of trypanosomes by Raman spectroscopy:
  - For each subject at each time point, one DBS from the field and one FFPE slide generated for IHC at IP Paris will be scanned by Raman spectroscopy at the University of Glasgow in the context of an exploratory procedure based on the measurements of biophysical parameters associated to the presence of trypanosomes.

• The results will not be uploaded in the central data base as the final analyses will rely on machine learning approaches after the end of the study.

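### The second-round accuracy table scores tests against a new reference built from those same tests, so components of that reference look better by construction

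*Protocol*

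**What the plan says.** Protocol 10.8 (Properties of diagnostic tests) has two rounds. In the first, the novel assays are compared at enrolment with TgSGP-PCR in skin and then with IHC, TBR-PCR and 18S-PCR, "to assess the specificity, sensitivity, positive and negative predictive values of the new qPCRs, multiplex RT-qPCRs, and SHERLOCK in blood and/or skin". Tests are next ranked on several criteria, starting with how well the month 4 result reproduces the baseline result in the placebo group. Combinations are candidates: "The test or combination of tests providing the best association (reproducibility of baseline result) will be used for ranking tests". The candidate with the best sum of ranks becomes the new reference, the primary analysis is repeated on it, and "each diagnostic test property will be computed with respect to this new reference".

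SAP 5.3.6 repeats the rule. It adds kappa to the ranking criteria and again admits combinations: "Cohen Kappa coefficient will also be used for ranking tests alone or in combination". It describes sensitivity, specificity and NPV as relative; PPV carries no such label.

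Neither document says how assays are combined. The nearest operational wording in SAP 5.3.6, "considering the result of any of the three samples", is an any-positive rule across sample types, and it belongs to the first-round analyses. Protocol 8.4 lists TgSGP-PCR as a follow-on test: "For TBR-PCR+ and/or 18S-PCR+ samples".

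**The concern.** A reference standard should not contain the result of the test it judges. Here the reference is by definition one of the scored tests or a combination of them, and nothing keeps its components out of the scoring. Some cells of the second-round table can therefore be filled in before any sample is analysed. Tests inside the winning combination would appear more accurate than equally good tests outside it. Comparing test properties is a stated exploratory objective, and a reader of the table could take that difference as evidence for choosing an assay.

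**Working it through.** The plan gives no figure on this point, so there is none to reproduce. The check is set logic, then an illustration of size.

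**Set logic (R is the new reference)**
- R = A or B: A+ implies R+, so A has PPV 100%. R− implies A−, so A has specificity 100%.
- R = A and B: R+ implies A+, so A has sensitivity 100%. A− implies R−, so A has NPV 100%.
- R = A: A scores 100% on all four. Any any-positive combination containing A has sensitivity and NPV of 100%.
- R = at least 2 of 3: nothing is forced to 100%.

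Accuracy does not enter the first three. An uninformative test (sensitivity 20%, specificity 80%) still gets 100% specificity and PPV as a component of an or-rule.

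**Inputs for size**
- Prevalence 20%: the planning value in Protocol 10.1.2.
- Assumed, not in the documents: every test has sensitivity 0.70 and specificity 0.97, with results independent given true status. C is always outside the reference.

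Any one test: P(+) = 0.2×0.70 + 0.8×0.03 = 0.164. True PPV = 0.140/0.164 = 85.4%; true NPV = 0.776/0.836 = 92.8%.

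**R = A or B**
- P(R+) = 0.2×(1−0.3²) + 0.8×(1−0.97²) = 0.1820 + 0.0473 = 0.2293.
- A: sensitivity = 0.164/0.2293 = 71.5%.
- C: P(C+,R+) = 0.2×0.70×0.91 + 0.8×0.03×0.0591 = 0.1288. Sensitivity = 0.1288/0.2293 = 56.2%; PPV = 0.1288/0.164 = 78.5%; specificity = 1 − (0.164−0.1288)/0.7707 = 95.4%.

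**R = A and B**
- P(R+) = 0.2×0.49 + 0.8×0.0009 = 0.0987.
- C: P(C+,R+) = 0.2×0.343 + 0.8×0.000027 = 0.0686. Sensitivity = 0.0686/0.0987 = 69.5%; PPV = 0.0686/0.164 = 41.8%.

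**R = at least 2 of A, B, E** (E is a third equal component)
- P(R+) = 0.2×0.784 + 0.8×0.002646 = 0.1589.
- A: P(A+,R+) = 0.1288. Sensitivity = 0.1288/0.1589 = 81.1%; PPV = 78.5%.
- C: P(C+,R+) = 0.2×0.70×0.784 + 0.8×0.03×0.002646 = 0.1098. Sensitivity = 0.1098/0.1589 = 69.1%; PPV = 0.1098/0.164 = 67.0%.

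| Reference | Test | Sens. | Spec. | PPV | NPV |
|---|---|---|---|---|---|
| True status | any | 70.0 | 97.0 | 85.4 | 92.8 |
| A or B | A (component) | 71.5 | 100 | 100 | 92.2 |
| A or B | C (outside) | 56.2 | 95.4 | 78.5 | 88.0 |
| A and B | A (component) | 100 | 92.8 | 60.2 | 100 |
| A and B | C (outside) | 69.5 | 89.4 | 41.8 | 96.4 |
| 2 of A, B, E | A (component) | 81.1 | 95.8 | 78.5 | 96.4 |
| 2 of A, B, E | C (outside) | 69.1 | 93.6 | 67.0 | 94.1 |

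**Sensitivity to the assumptions (R = A or B; A's PPV stays at 100%)**
- Prevalence 5%: C's PPV is (0.05×0.70×0.91 + 0.95×0.03×0.0591)/0.0635 = 52.8%.
- Specificity 0.99, prevalence 20%: C's PPV is 86.2%.
- Positive dependence, modelled as a shared normal latent factor within each true status: with latent correlation 0.5 and 0.8, C's PPV rises to about 83% and 90% at prevalence 20%, and to about 65% and 80% at prevalence 5%. C's specificity at prevalence 20% rises to 96.5% and 97.9%.

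**Nesting.** TgSGP-PCR is listed only for samples positive by TBR-PCR or 18S-PCR. Against a TBR-or-18S reference in the same sample type, every TgSGP positive is a reference positive, so its PPV is 100%. Its specificity is 100% if samples not run count as negative, and has no denominator if they count as missing. This happens although TgSGP-PCR is not itself part of that reference.

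**The case against.** The strongest reply is that little depends on this table. The first-round comparison against TgSGP-PCR, and then IHC, TBR-PCR and 18S-PCR, is still reported, and the SAP's objective describes the comparison as one with a gold-standard PCR. The ranking, the choice of reference and the repeated treatment comparison all come before any second-round property exists. The sub-study is labelled exploratory, and the SAP uses the word relative. Exact 100% values need a single winner or a pure or-rule or and-rule, and no rule is stated. A single test scoring 100% against itself would mislead nobody. The table shells are a separate attachment and might already blank such cells. The assays share extracted nucleic acids (Protocol 8.4), so positive dependence is plausible and the gap smaller than under independence.

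Most of this stands as a limit on consequence. It does not remove the defect. The relative label concedes an imperfect reference, not one that contains the test being scored, and PPV lacks the label altogether. A two-of-three rule still favours components. Dependence shrinks the gap without closing it. What the shells contain is only a possibility. A PPV of 100% for one component among many tests is not obviously an artefact.

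**Conclusion.** The point holds for the second-round accuracy table. As written, the rule gives component tests forced or favoured values relative to equally accurate tests outside the reference. The forced values follow from logic alone under an or-rule, an and-rule or a single-test winner. In the or-rule illustration, the PPV gap at 20% prevalence runs from 21.5 points (100 − 78.5) under independence to about 10 points under strong positive dependence. At 5% prevalence it runs from 47.2 points (100 − 52.8) to about 20. These sizes rest on assumed accuracies and an assumed combination rule.

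A reader might infer that the whole comparison of methods, the choice of the new reference or the repeated efficacy analysis is fixed by construction. The documents do not support that: the first round stands separately, and no text feeds second-round values back into the ranking or the treatment comparison. The effectiveness objective does depend on a method having better validity than TgSGP-PCR, but neither document says which round supplies that judgement, so a link cannot be asserted.

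**What to change.** Amend Protocol 10.8 and SAP 5.3.6 in the same way:

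1. State in advance how assays and sample types are combined (any positive, all positive, or at least k of n).
2. Report second-round sensitivity, specificity, PPV and NPV only for tests and combinations that share no assay result with the new reference and are not nested in it by reflex testing. Name the TgSGP-PCR and TBR-PCR/18S-PCR case explicitly.
3. For overlapping tests, print 'not applicable - part of reference', with a matching label for nested tests.
4. If a figure for a component is wanted, score it against the reference rebuilt without that assay, as a separate, labelled supplementary result. It must not be ranked with the others, because each component would then be judged against a different yardstick.

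This removes the values fixed by construction; it does not make the new reference a gold standard. The cost is a few sentences, including the combination rule that is missing now, and some code. No new data are needed. Some accuracy cells will be dropped or become less favourable.
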